## Summaries of Treatment Group Comparability

Demographics and baseline characteristics (including age, sex, medical history, randomization stratification factors) will be summarized descriptively by treatment arm as assigned for both the CSF-mITT analysis set and the CSF-longitudinal analysis set (see [Table 2](#)) using:

- means, SDs, medians, and ranges for continuous variables
- counts and proportions for categorical variables

## Visit Windowing

For CSF assessments time windows based on study days, as defined in [Table 10](#), will be used. Study days are defined based on days on study since the date of the first dose, with the day of the first dose being Study Day 1.

**Table 10 Time Windows for CSF Assessments**

Visit	Target study day	Time window
Baseline	1	Up to day 35
Week 116	813	645, 897

### 5.7.8 Plasma Biomarker Analyses

Plasma biomarkers will be analyzed separately for each study (GRADUATE I and GRADUATE II).

Analysis of plasma biomarkers will be based on the ITT analysis set unless otherwise specified.

The plasma biomarkers will be summarized by treatment group and visit (see schedule of assessment in the study protocol).

*For each plasma biomarker, two statistically equivalent MMRM models will be considered:*

1. *using the change from baseline as dependent variable, with covariates: treatment arm (as categorical), visit (as categorical), treatment-by-visit interaction, APOE ε4 status (as categorical; carrier vs non-carrier), baseline biomarker and baseline biomarker-by-visit.*
2. *using the value at the post-baseline visit as the dependent variable, with covariates: treatment arm (as categorical), visit (as categorical), treatment-by-visit interaction, APOE ε4 status (as categorical; carrier vs non-carrier), baseline biomarker and baseline biomarker-by-visit.*

*For both models, visit will be treated as the repeated variable within a participant. An unstructured variance-covariance matrix will be applied to model the within-participant errors; in case of non-convergence, compound symmetry will be used, together with a robust estimator of standard error (“sandwich” estimator).*

*Both models will use log (base 10) transformed biomarker data. The following summary statistics will be estimated after the appropriate back-transformation of the original model parameters:*

- The geometric mean at each visit for each treatment arm, obtained as  $10^{\text{LSM}}$ , where LSM is the least square mean for the corresponding treatment arm at the corresponding visit based on model 2.*
- The geometric mean ratio (gantenerumab relative to placebo) at each visit, obtained as  $10^{\text{LSM\_GvsP}}$ , where LSM\_GvsP is the least square means of the contrast of Gantenerumab against placebo at the corresponding visit based on model 2.*
- The %-difference in geometric mean (relative to placebo) at each visit, obtained as  $[(10^{\text{LSM\_GvsP}}) - 1] * 100$ , at the corresponding visit, based on model 2.*
- The %-change from Baseline to each visit in the Geometric Mean, obtained as  $[10^{\text{LSM}} - 1] * 100$ , where LSM is the least square mean for the corresponding treatment arm at the corresponding visit based on model 1.*

There will be no data imputation for missing data. However, the MMRM provides unbiased estimates and valid inference in the presence of missing data, under the MAR (missing at random) assumption.

The following plasma biomarkers will be analyzed:

- Amyloid beta (1-42) (Abeta-42)
- Phosphorylated tau (pTau-181)

Other exploratory plasma biomarkers may be reported separately.

### **Summaries of Treatment Group Comparability**

Demographics and baseline characteristics (including age, sex, medical history, randomization stratification factors) will be summarized descriptively by treatment arm as assigned for both the ITT analysis set and the Plasma-longitudinal analysis set (see [Table 2](#)) using:

- means, SDs, medians, and ranges for continuous variables
- counts and proportions for categorical variables

### **Visit Windowing**

For Plasma assessments time windows based on study days, as defined in [Table 11](#), will be used. Study days are defined based on days on study since the date of the first dose, with the day of the first dose being Study Day 1.

**Table 11 Time windows for Plasma assessments**

Visit	Target study day	Time window
Baseline	1	Up to Day 35
Week 24	169	85, 253
Week 52	365	281, 449
Week 104	729	645, 770
Week 116	813	771, 897

### **5.7.9 Volumetric MRI Analyses**

Structural MRI will be analyzed separately for each study (GRADUATE I and GRADUATE II).

Analysis of structural MRI (volumetric MRI) will be based on the MRI-mITT analysis set unless otherwise specified.

Volumetric MRI, for each brain region, will be summarized by treatment group and visit using descriptive statistics for the absolute volume at baseline and percent change from baseline at post-baseline visits.

An MMRM analysis will be used to estimate the mean percent change from baseline to Week 116 (as well Week 48 and 104) in Volumetric MRI for each brain region. The model will include the percent change from baseline in volumetric MRI as the dependent variable, while adjusting for treatment arm (as categorical), visit (as categorical), treatment-by-visit interaction, baseline age, gender (as categorical), APOE ε4 status (as categorical; carrier vs. non-carrier) and disease stage (as categorical). Visit will be treated as the repeated variable within a participant. An unstructured variance-covariance matrix will be applied to model the within-participant errors; in the case of non-convergence, compound symmetry will be used, together with a robust estimator of standard error (“sandwich” estimator).

There will be no data imputation for missing data. However, the MMRM provides unbiased estimates and valid inference in the presence of missing data, under the MAR (missing at random) assumption.

The following brain regions will be considered:

- Whole brain
- Ventricles

- Hippocampus right and left
- Cortical gray matter

Other exploratory analyses based on other brain regions may be reported separately.

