**5.7.5.5 Main Analytical Approach**

An MMRM will be used to estimate the mean change in Centiloid from baseline to Week 116 within each of the substudies. The model will include the change from baseline in Centiloids as the dependent variable, while adjusting for treatment arm (as categorical), visit (as categorical), APOE ε4 status (as categorical; carrier vs non-carrier), type of tracer (as categorical; Florbetaben vs Flutemetamol), baseline Centiloid, baseline Centiloid-by-visit and treatment-by-visit interaction. Visit will be treated as the repeated variable within a participant. An unstructured variance-covariance matrix will be applied to model the within-participant errors; in the case of non-convergence, compound symmetry will be used, together with a robust estimator of standard error (“sandwich” estimator).

In line with the estimand definition, data acquired after the ICE “Substantial reduction in drug exposure due to the COVID-19 pandemic” (as defined in [Table 3](#)) or more than 56 days from treatment discontinuation will be excluded from the analysis and treated as missing for the primary analysis purposes.

There will be no data imputation for missing data. However, the MMRM provides unbiased estimates and valid inference in the presence of missing data, under the MAR (missing at random) assumption.

The difference in least squares means between active drug and placebo arms at Week 116 will be estimated and presented alongside p-value and the 95% confidence interval for treatment difference. A p-value <0.0001 will be regarded as a statistically significant evidence, irrespective of the results of the other primary/secondary endpoints

(along the lines of the [Haybittle–Peto](#) rule, and thus maintaining the overall type-I error within the study).

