### **5.7.6.3 Main Analytical Approach**

An MMRM analysis will be used to estimate the mean change from baseline to Week 116 for each of the median SUVRs defined. The model will include the change from baseline in median SUVR as the dependent variable, while adjusting for treatment arm (as categorical), visit (as categorical), APOE  $\epsilon 4$  status (as categorical; carrier vs non-carrier), baseline median SUVR, baseline median SUVR-by-visit, study, study-by-visit and treatment-by-visit interaction. Visit will be treated as the repeated variable within a participant. An unstructured variance-covariance matrix will be applied to model the within-participant errors; in the case of non-convergence, compound symmetry will be used, together with a robust estimator of standard error (“sandwich” estimator).

In line with the estimand definition, data acquired after the ICE “Substantial reduction in drug exposure due to the COVID-19 pandemic” (as defined in [Table 3](#)) or more than 56 days from last dose will be excluded from the analysis and treated as missing for the primary analysis purposes.

There will be no data imputation for missing data. However, the MMRM provides unbiased estimates and valid inference in the presence of missing data, under the MAR (missing at random) assumption. A subgroup analysis by parent study may be also considered in order to derive a study-specific treatment effect.

Based the same MMRM model already described in this section, the change from baseline to week 52 in tau PET will also be reported as supplementary analysis.

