### **5.7.7 Cerebrospinal Fluid (CSF) Analyses**

The main analysis for the CSF biomarkers will be based on the pooled dataset of GRADUATE I and GRADUATE II studies (due to the small number of CSF samples within each study). Analyses at individual study level will be conducted as well.

Analysis of CSF biomarkers will be based on the CSF-mITT analysis set unless otherwise specified.

CSF biomarker data will be summarized by treatment group and visit (see schedule of assessment in the study protocol).

*For each CSF biomarker, two statistically equivalent ANCOVA models will be considered:*

- 1. using the change from baseline to Week 116 as dependent variable, with covariates: treatment arm (as categorical), APOE ε4 status (as categorical; carrier vs non-carrier) and baseline biomarker.*
- 2. using the value at Week 116 as the dependent variable, with covariates: treatment arm (as categorical), APOE ε4 status (as categorical; carrier vs non-carrier) and baseline biomarker.*

Both models will use log (base 10) transformed biomarker data. The following summary statistics will be estimated after the appropriate back-transformation of the original model parameters:

- The geometric mean at Week 116 for each treatment arm, obtained as  $10^{\text{LSM}}$ , where LSM is the least square mean for the corresponding treatment arm based on model 2.
- The geometric mean ratio (gantenerumab relative to placebo) at week 116, obtained as  $10^{\text{LSM\_GvsP}}$ , where LSM\_GvsP is the least square means of the contrast of Gantenerumab against placebo based on model 2.
- The %-difference in geometric mean (relative to placebo) at week 116, obtained as  $[(10^{\text{LSM\_GvsP}}) - 1] * 100$  based on model 2.

- *The %-change from Baseline to Week 116 in the Geometric Mean for each treatment arm, obtained as  $[10^{LSM} - 1] * 100$ , where LSM is the least square mean for the corresponding treatment arm at the corresponding visit based on model 1*

There will be no data imputation for missing data.

The following CSF biomarkers will be analyzed:

- Total tau (tTau)
- Phosphorylated tau (pTau-181)
- Neurogranin
- Neurofilament light (NFL)

Other exploratory CSF biomarker may be reported separately.

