**Table 12 Time windows for Volumetric MRI assessments**

Visit	Target study day	Time window
Baseline	1	Up to Day 35
Week 48	337	253, 421
Week 104	729	645, 770
Week 116	813	771, 897

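### The exploratory volumetric MRI model leaves out the baseline volume of the region analysed, although the SAP's other biomarker and clinical change models adjust for their own baseline

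*SAP*

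**What the plan says.** SAP Section 5.7.9 plans one MMRM per brain region (whole brain, ventricles, right and left hippocampus, cortical gray matter). "The model will include the percent change from baseline in volumetric MRI as the dependent variable, while adjusting for treatment arm (as categorical), visit" begins the covariate list. The rest of the list is the arm-by-visit interaction, baseline age, gender, APOE ε4 status and disease stage. Baseline volume appears only as the denominator of percent change and in the summaries, which give "descriptive statistics for the absolute volume at baseline and percent change from baseline at post-baseline visits". Missing scans are not imputed. The section relies on the statement that "the MMRM provides unbiased estimates and valid inference in the presence of missing data, under the MAR (missing at random) assumption".

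The other biomarker models each carry their own baseline:

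- Amyloid PET (5.7.5.5): "baseline Centiloid, baseline Centiloid-by-visit and treatment-by-visit interaction".
- Tau PET (5.7.6.3): "baseline median SUVR, baseline median SUVR-by-visit, study, study-by-visit and treatment-by-visit interaction".
- CSF (5.7.7), a single-visit ANCOVA: "carrier vs non-carrier) and baseline biomarker". On scale, 5.7.7 says "Both models will use log (base 10) transformed biomarker data".
- Plasma (5.7.8): baseline biomarker and its interaction with visit, also on the log scale.

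The clinical models do the same: the primary imputation and analysis models (5.3.3), the supplementary MMRM (5.3.5.2), and the secondary and continuous exploratory endpoints (5.4, 5.5).

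Volumetric MRI is listed as exploratory in SAP Table 1 and Protocol Table 2. It is not in the testing hierarchy of SAP 5.1.

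**The concern.** A baseline measurement of the outcome is usually the first covariate to consider in a change-from-baseline model. Dividing by baseline does not remove the dependence on it. If follow-up volume is roughly a + b × baseline, percent change contains a term 100 × a / baseline, which disappears only when a = 0. Measurement error in the baseline scan also links percent change to baseline.

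If that dependence remains after age, gender, APOE ε4 status and disease stage, the planned model leaves explainable variance in the residual and does not correct chance baseline imbalance. The regional contrasts would then have wider confidence intervals than the collected data allow. The missing-at-random assumption would also be stronger than it needs to be, because the model does not allow missingness to depend on baseline volume.

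**Working it through.** **There is no stated figure to reproduce.** No sample size, power or alpha in the documents depends on this choice.

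**Precision, complete data.** The one input is r, the partial correlation of baseline volume with percent change given the other covariates. The documents do not give it, so it is assumed over a range. In large samples:

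variance with the term / variance without it = 1 − r²; reduction in standard error = 1 − √(1 − r²).

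| Assumed r | 1 − r² | SE ratio | SE reduction |
|---|---|---|---|
| 0.1 | 0.99 | 0.995 | 0.5% |
| 0.2 | 0.96 | 0.980 | 2.0% |
| 0.3 | 0.91 | 0.954 | 4.6% |
| 0.4 | 0.84 | 0.917 | 8.3% |

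A simulation of 4,000 trials per value of r, with 508 per arm and complete data, gave variance ratios of 0.999, 0.992, 0.959 and 0.912 for r = 0, 0.1, 0.2 and 0.3. These agree with the formula. Both estimators were unbiased (mean error about 0.001), and at r = 0 the extra term cost nothing measurable.

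**Who may have no post-baseline volume in the model.** "Table 12 Time windows for Volumetric MRI assessments" gives windows of Days 253–421 (Week 48), 645–770 (Week 104) and 771–897 (Week 116). Study day = 7 × week + 1.

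- Protocol 4.7.1 follows participants who withdraw from treatment without further MRI, but first brings them back for an early-termination visit 2 weeks after the last dose. Appendix 1 schedules an MRI at that visit.
- Last dose at Week 32: visit at Week 34, Day 7 × 34 + 1 = 239, before the first window. Next scheduled dose, Week 36: visit at Week 38, Day 267, inside it. The boundary is a last dose at Week 34: visit at Week 36, Day 253.
- Earlier safety scans do not help. The last is due at least 7 days before the Week 36 dose (Day 253), so by Day 246.
- A last dose between Week 34 and Week 58 puts the early-termination scan at Weeks 36 to 60, Days 253 to 421, inside the Week 48 window. A last dose from Week 90 puts it at Week 92, Day 645, where the Week 104 window opens.

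So participants who withdraw before about Week 34 to 36 generally have no in-window scan unless an unscheduled one supplies it. Later withdrawers may have one. Section 5.7.9 does not say that early-termination scans are assigned by window, as 5.7.5.3 does for amyloid PET, but its windows are defined by study day and would admit them.

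**The case against.** The strongest reply is that percent change already scales by baseline and that the MRI covariate list looks deliberate. It adds age, gender and disease stage, which none of the other four biomarker models uses and which may carry part of what baseline volume would.

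The comparison with the other models is also imperfect. Amyloid and tau PET use absolute change. CSF and plasma are each fitted twice, once on change and once on value at visit, and the SAP wants the two fits to agree exactly. That requires baseline in both, whereas MRI has only one model.

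These points weaken the analogy, and the partial correlation may well be small. They give no reason to leave the term out, and the SAP states none. A sentence of rationale would answer the lack of explanation, but it would not recover any precision.

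A reader might go further and infer that the omission biases the MRI contrast through dropout. The documents do not support that. They give no rate of missing MRI, and nothing shows that dropout depends on baseline volume, still less that it does so differently by arm. The scheduled early-termination MRI also supplies in-window data for many later withdrawals. Any size put on such a bias would rest entirely on invented inputs.

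**Conclusion.** The point holds as a modest, free improvement. Section 5.7.9 is out of line with the SAP's other change-from-baseline models, without explanation. The likely cost is precision: 0.5% to 8.3% of the standard error for an assumed partial r of 0.1 to 0.4, and nothing if r is zero. These figures assume complete data and a correlation that the documents do not supply.

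The missing-data benefit is secondary and is not quantified. Adding the term would let missingness depend on baseline volume, which matters mainly for early withdrawers with no in-window scan. It helps only if baseline volume predicts both missingness and the missing percent change after the other covariates and any earlier scans.

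Nothing here makes the planned analysis invalid. The endpoint is exploratory and outside the testing hierarchy, so the primary conclusion, type I error control and sample size do not change.

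**What to change.** In SAP 5.7.9, add the baseline volume of the analysed region and its interaction with visit to the MMRM covariates, in the form already used for amyloid PET, tau PET and plasma. Make the change before unblinding, so that there is no choice between adjusted and unadjusted MRI results once the data are seen.

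The cost is a line of SAP wording and one covariate with its visit interaction. No new data are needed, because baseline volume is already measured and summarised. No participant is lost: percent change cannot be computed without a baseline volume, and SAP 5.1 already excludes participants with no baseline outcome from change-from-baseline models.

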### **Summaries of Treatment Group Comparability**

Demographics and baseline characteristics (including age, sex, medical history, randomization stratification factors) will be summarized descriptively by treatment arm as assigned for both the MRI-mITT analysis set and the MRI-longitudinal analysis set (see [Table 2](#)) using:

- means, SDs, medians, and ranges for continuous variables
- counts and proportions for categorical variables

### **Visit Windowing**

For Volumetric MRI assessments time windows based on study days, as defined in [Table 12](#), will be used. Study days are defined based on days on study since the date of the first dose, with the day of the first dose being Study Day 1.

**Table 12 Time windows for Volumetric MRI assessments**

Visit	Target study day	Time window
Baseline	1	Up to Day 35
Week 48	337	253, 421
Week 104	729	645, 770
Week 116	813	771, 897

## **5.8 INTERIM ANALYSES**

Details of interim analysis plans are described in a separate interim analysis SAP (iSAP), providing information about a futility interim analysis based on the primary efficacy endpoint CDR-SB.

Other than the futility analysis, there is no plan for an efficacy interim analysis based on the primary endpoint. The primary analysis of the clinical efficacy endpoints will be performed only once, after completion of the efficacy data collection at the end of the double blind part of the study (as described in this SAP) and it will be the only opportunity to formally reject the primary null hypothesis of the trial.

## **6. SUPPORTING DOCUMENTATION**

This document is part of a broader Data Analysis Plan that has several documents, including:

- Graduates studies interim analysis SAP
- Graduates studies Data Analysis Plan Module 2
- Graduates studies Data Analysis Plan Module 3

# Appendix 1 Type I Error Control Considerations for Reference-Based Conditional Mean Imputation Combined with the Jackknife for Inference

## Introduction

In the GRADUATE trials, hypothetical and treatment policy strategies are applied to Non Study Drug or Condition Related (NSDCR) intercurrent events (ICEs) and Study Drug or Condition Related (SDCR) ICEs, respectively. That is, the clinical interest is in a scenario where SDCR ICEs but not NSDCR ICEs do occur. For estimating the treatment effect, data after NSDCR are assumed to be missing at random (MAR) whereas missing data after SDCR are imputed based on the placebo group in both treatment groups using the copy-increments-in-reference (CIR) imputation method, a specific type of reference-based imputation. We refer to Section 5.3.3 for further details.

The primary analysis of the GRADUATE trials is implemented using conditional mean imputation of missing data combined with the jackknife for inference. This methodology has been described and justified in Wolbers et al. (2022). In this appendix, we provide further details regarding type I error control of the method including additional simulations targeted to the setting of the GRADUATE trials.

## Theoretical and published simulation evidence for type I error control

As demonstrated in Section 2.5 of Wolbers et al. (2022), the proposed conditional mean imputation methodology corresponds to a computationally efficient implementation of maximum likelihood multiple imputation. Estimators based on maximum likelihood imputation are asymptotically normal and unbiased if the imputation model and the associated missing data assumptions are correctly specified (Wang and Robins (1998), Robins and Wang [2000]). Moreover, standard error estimates based on resampling methods such as the jackknife or the bootstrap are consistent (Bartlett and Hughes (2020), von Hippel and Bartlett (2021), Wolbers et al. (2022)).

Therefore, large-sample (asymptotic) type I error control is guaranteed if the imputation model and the associated missing data assumptions are correctly specified. This is the case if the following conditions hold:

- All ICEs are correctly identified and classified as NSDCR or SDCR.
- Observed outcome data prior to an ICEs follow a multivariate normal mixed model for repeated measures (MMRM) with an unstructured covariance matrix.
- Missing outcome data prior to an ICE are missing at random (MAR).
- Missing outcome data after NSDCR ICEs compatible with a hypothetical strategy is also MAR.
- Missing outcome data after SDCR ICEs are compatible with the copy-increments-in-reference (CIR) assumption.

In contrast, the commonly used MMRM model requires that all missing data are MAR (Mallinckrodt et al. [2008]). In many settings, a reference-based missing data assumption for SDCR ICEs such as CIR is arguably more plausible and conservative than the MAR assumption of the classical MMRM model.

In order to study type I error control for finite sample sizes, simulation studies are required. A simulation study reported in Wolbers et al. (2022) assessed type I error via simulation (based on 100,000 simulations) for a setting with a relatively low sample size (100 subjects per group), a large proportion of ICEs (34% and 24% in the active and placebo groups, respectively), and a large probability of study drop-out after the occurrence of the ICE of 75%. For standard MAR and all reference-based imputation methods, inference based on conditional mean imputation and jackknifing strictly protected type I error. Simulation results reported in Liu and Pang (2016) for a similar method also found no evidence of type I error inflation for reference-based methods or the MMRM model if the missing data mechanism was correctly specified. These simulation results are also consistent with simulation studies which report that the MMRM model (or an asymptotically equivalent multiple imputation model) provides adequate type I error control if all missing data are MAR (Siddiqui [2011], Lu and Mehrotra [2010]).

In contrast, statistical methods cannot be expected to strictly control type I error if the missing data assumptions are not correctly specified. For example, simulations reported in Liu and Pang (2016) demonstrate type I error inflation for both reference-based methods and the MMRM model if missing data are simulated under certain missing not at random (MNAR) scenarios. Similarly, Mallinckrodt et al. (2004) demonstrated type I inflation of the MMRM model under MNAR scenarios but type I error control of the MMRM model was much closer to nominal values compared to naive approaches to missing data such as the last observation carried forward (LOCF) approach. Whether or not the missing data assumptions is correctly specified is by nature something that cannot be verified

In conclusion, reference-based imputation methods based on conditional mean imputation and jackknifing control type I error if the imputation model and the associated missing data assumptions are correctly specified. Neither reference-based imputation methods nor the MMRM model can guarantee strict type I error control if the missing data assumptions are not correctly specified. Therefore, sensitivity analyses such as tipping point analyses should always be performed to assess the robustness of the results to deviations from the missing data assumptions.

